### 6.3.2. Secondary Efficacy Analysis

The above secondary efficacy variables will be analyzed in the similar way as the primary analysis for the primary efficacy variable.

- Change from baseline to weeks 1, 2, 3 and 4 in the weekly average of the average pain score recorded in the evening
- Change from baseline to weeks 1, 2, 3 and 4 in the weekly average of the average pain score recorded in the morning

- Change from baseline to weeks 1, 2, 3 and 4 in the weekly average of the worst pain score recorded in the evening (worst pain is defined as the patient-reported worst pain intensity over the prior 24 hours)
- Change from baseline (randomization visit) to weeks 2 and 4 in the NPSI score
- Change from baseline (randomization visit) in DSIS scores at weeks 2 and 4
- Change from baseline (randomization visit) to weeks 2 and 4 in maximal intensity of patients' brush-evoked allodynia, as measured on the 11-point NRS
- Change from baseline (randomization visit) to weeks 2 and 4 in maximal intensity of patients' punctate-evoked hyperalgesia using a Medipin, as measured on the 11-point NRS

In addition, the following analyses will be done:

[figure not shown]
- Percentage of patients with  $\geq 30\%$  improvement and  $\geq 50\%$  improvement from baseline in the weekly average of the daily average NRS scores at week 4 will be analyzed using logistic regression model with pooled study center, treatment as fixed factors and baseline NRS scores as covariate.
- Time to reach  $\geq 30\%$  sustained improvement from baseline in the weekly average of the daily average NRS scores will be summarized using Kaplan-Meier method.
- Patients' global assessment of treatment, as measured by PGIC scores, at weeks 2 and 4 will be analyzed using a MMRM model similar to the primary efficacy variable with pooled study center, week, treatment, and treatment by week interaction as fixed factors and patient as a random factor. The unstructured covariance matrix for repeated observations within patients will be used.
- Change from baseline (randomization visit) to week 4 in the NePIQoL score will be analyzed using an analysis of covariance (ANCOVA) model with pooled study center, treatment as fixed factors and baseline value as covariate. The missing week 4 values will be imputed using last observation carried forward (LOCF) method.

[figure not shown]
SAS code for ANCOVA model

[figure not shown]
```
Proc mixed data=datain order=data;
  Class center treatment;
  Model change = base center treatment;
  Lsmean treatment /pdiff cl ;
  Run;
```

[figure not shown]
A descriptive summary of the secondary efficacy variables will be provided by treatment group for scheduled visits. Change from baseline will be provided for continuous variables.

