9.6.1.3. Secondary Efficacy Analysis

The continuous secondary efficacy variables will be analyzed in a similar way as the primary efficacy variable.

The percentages of patients with $\geq 30\%$ and $\geq 50\%$ improvement from baseline in weekly average NRS scores at week 4 will be summarized using descriptive statistics. The time to reach $\geq 30\%$ improvement in weekly average NRS scores from baseline will also be summarized using descriptive statistics.

PGIC scores will be analyzed using a MMRM model with week, treatment, and treatment by week interaction as fixed factors and patient as a random factor. The unstructured covariance matrix for repeated observations within patients will be used.

NePIQoL score will be analyzed using an analysis of covariance (ANCOVA) model with effects due to baseline and treatment, imputing missing data via last observation carried forward (LOCF).

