#### 6.2.2. Primary Analysis

The primary efficacy variable for this study is the change from baseline to week 4 in the weekly average of the daily average NRS pain scores. This variable will be analyzed using a Mixed Model Repeated Measures (MMRM) model with change from baseline in the weekly average of the daily average NRS scores at weeks 1, 2, 3 and 4 as the dependent variable; week, pooled study center, treatment, and treatment by visit interaction as fixed factors, baseline weekly average of the daily average NRS scores as covariate; and patient as a random effect. The unstructured covariance matrix for repeated observations within patients will be used. If the model does not converge, the maximum-likelihood (ML) estimation method will be used instead of the default restricted ML (REML) method. If the model still does not converge, then simpler covariance structures with less parameters will be used in the following order until the model does converge: heterogeneous autoregressive (1) (ARH[1]); heterogeneous compound symmetry (CSH); autoregressive (1) (AR[1]); and compound symmetry (CS). The primary treatment comparison will be conducted at week 4 in this model.

The least square (LS) means and standard error of each treatment group, LS means differences including standard error, 95% confident interval (CI) and p-values, between each active group and the placebo group for the change from baseline to weeks 1, 2, 3 and 4 in the weekly average of the daily average NRS pain scores will be presented in the tables.

SAS code for primary endpoint:

```

Proc mixed data=datain;
Class treatment week patient;
Model change=base treatment center week treatment*week/ddfm=kr;
Repeated week/sub=patient type=un;
Lsmean treatment*week/pdiff cl ;
*** treatment order in the data will be placebo, 4%, 8%*****;

Estimate '4% vs. Placebo at week 4' treatment -1 1 0 treatment*week 0 0 0 -1
0 0 0 1 0 0 0 0/ cl;
Estimate '8% vs. Placebo at week 4' treatment -1 0 1 treatment*week 0 0 0 -1
0 0 0 0 0 0 1/cl;

Run;

```

A descriptive summary of the weekly average of the daily average NRS pain scores at baseline, weeks 1, 2, 3 and 4, as well as the change from baseline will be provided by treatment group.

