- NePQoL is a questionnaire that contains 41 items to evaluate quality of life in patients with neuropathic pain. Each question has responses ranging from strongly agree or always to strongly disagree or never. Questions are scored on a 5-point scale from 1 to 5, where higher scores represent greater pain-related interference in the quality of life (four items will have scores inverted so that higher scores reflect greater pain. “I involve myself with people I am close to as much as I used to despite the pain”, “I can distract myself from the pain”, “I can cope with the pain”, and “I still enjoy my hobbies/leisure activities despite the pain.”). The total score is calculated as the sum of the scores for the individual questions (Poole and Nurmikko 2009). If scores for up to 4 questions are missing then the total score will be computed as 41 times sum of non-missing scores divided by the number of non-missing questions. If responses for more than 4 questions are missing then the total score will be considered missing.
- PGIC is a standardized self-report tool that measures the change in a patient's overall status rating since the start of treatment (Hurst and Bolton 2004) on 7-point scale. The 7-point scale is defined as: 1=very much improved, 2=much improved, 3=minimally improved, 4=no change, 5=minimally worse, 6=much worse, 7=very much worse.
- DSIS is an 11-point scale that asks the patient to “select the number that best describes how much your pain has interfered with your sleep during the past 24 hours.” Response options range from 0 (Did not interfere with sleep) to 10 (Completely interfered with sleep/unable to sleep due to pain).
- First time to reach  $\geq 30\%$  sustained improvement from baseline in the weekly average of the daily average NRS scores will be computed in days from the date of first dose, where the date of first dose is day 1. Those who do not achieve  $\geq 30\%$  sustained improvement from baseline will be censored at date of last dose of study medication. Sustained improvement is defined as an improvement of  $\geq 30\%$  that is maintained until the end of the treatment period.
- Maximal intensity of patients' brush-evoked allodynia, as measured on the 11-point NRS.
- Maximal intensity of patients' punctate-evoked hyperalgesia, as measured on the 11-point NRS using a Medipin.

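### The PGIC model is the only tested primary or secondary model with listed terms that has no baseline covariate, although baseline NRS pain is available and already used elsewhere

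*SAP*

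**What the plan says.** The SAP (6.3.1) describes PGIC as a 7-point rating of "the change in a patient's overall status rating since the start of treatment", so it cannot have a pre-treatment value. SAP 6.3.2 fits the week 2 and week 4 scores with an MMRM "with pooled study center, week, treatment, and treatment by week interaction as fixed factors and patient as a random factor". Protocol 9.6.1.3 has the same structure without center: "PGIC scores will be analyzed using a MMRM model with week, treatment, and treatment by week interaction as fixed factors". Neither list contains a baseline term. SAP 6.3.2 nevertheless describes the PGIC model as similar to that for the primary variable, and SAP section 10 does not comment on the difference.

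The other tested models do adjust for baseline:

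- Primary MMRM (SAP 6.2.2): "baseline weekly average of the daily average NRS scores as covariate".
- 30% and 50% responders (SAP 6.3.2): "logistic regression model with pooled study center, treatment as fixed factors and baseline NRS scores as covariate".
- NePIQoL (SAP 6.3.2): "analysis of covariance (ANCOVA) model with pooled study center, treatment as fixed factors and baseline value as covariate".
- Evening, morning and worst pain, NPSI, DSIS, allodynia and hyperalgesia (SAP 6.3.2): "The above secondary efficacy variables will be analyzed in the similar way as the primary analysis for the primary efficacy variable".

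Time to sustained 30% improvement is only summarized by Kaplan-Meier, with no tested model.

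**The concern.** When an outcome has no baseline value of its own, a related baseline measure can take its place. Here the obvious one is baseline NRS pain, which SAP 4.2 already derives from days -7 to -1. Inclusion criterion c requires at least 5 of 7 morning and 5 of 7 evening diary entries in that week, so essentially every eligible patient will have it.

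Two things are at stake, both conditional. If baseline pain predicts PGIC, leaving it out leaves explainable variance in the residual and widens the confidence interval. If the chance of dropping out depends on baseline pain and that dependence differs between arms, the patients who supply PGIC data are no longer balanced on a prognostic variable, and a model without that variable cannot correct for it.

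PGIC has less other protection than the primary endpoint. It is scheduled only at weeks 2 and 4, whereas the primary model uses weeks 1 to 4. The sensitivity analyses in SAP 6.2.3 cover the primary variable only. PGIC is also collected at the early termination visit (Protocol 3.11.3.4), but SAP 4.5 assigns those data to last-visit summaries and does not place them in the week 2 and week 4 model.

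**Working it through.** **1. Baseline covariate by tested model**

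| Endpoint | Method | Baseline covariate |
|---|---|---|
| Primary NRS change | MMRM | Baseline NRS (stated) |
| 30% and 50% responders | Logistic | Baseline NRS (stated) |
| NePIQoL | ANCOVA | Baseline value (stated; read as its own) |
| Evening, morning and worst pain, NPSI, DSIS, evoked pain | As the primary | Implied; most naturally each endpoint's own |
| PGIC | MMRM | None |

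**2. The plan's own figure.** Protocol 9.2 and SAP 2.3 give 88 completers per arm for the primary endpoint: difference 1.0, SD 2.35, 80% power, 2-sided 5%.

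- Normal approximation: n = 2 × [2.35 × (1.960 + 0.842) / 1.0]² = 86.7, so 87. The t-test version gives 87.66, so 88. The figure reproduces.
- Power at 88 is 80.6% (normal) or 80.2% (t).
- 88 / (1 − 0.20) = 110 randomized per arm, as stated.

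The documents give no PGIC figure. The 88 is used below only as a yardstick.

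**3. Precision.** Let r be the correlation of baseline NRS with PGIC. The documents do not give it, so a range is assumed.

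- Variance ratio, adjusted to unadjusted = 1 − r²
- Standard error ratio = √(1 − r²)
- Equivalent size = 88 / (1 − r²)

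| r | Variance saved | SE ratio | 88 per arm behaves like | Power, for an effect with 80.6% unadjusted |
|---|---|---|---|---|
| 0 | 0% | 1.000 | 88.0 | 80.6% |
| 0.1 | 1% | 0.995 | 88.9 | 81.0% |
| 0.2 | 4% | 0.980 | 91.7 | 82.1% |
| 0.3 | 9% | 0.954 | 96.7 | 84.1% |
| 0.5 | 25% | 0.866 | 117.3 | 90.3% |

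The gain at r of 0.1, 0.2 and 0.3 is therefore about 0.9, 3.7 and 8.7 patients per arm.

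**4. Dropout.** A large-sample simulation compared two arms with no true treatment effect and 20% dropout in each, with dropout depending on baseline pain only. Further assumptions were a correlation of 0.7 between week 2 and week 4 PGIC, and the same r at both weeks. The slope of dropout on baseline pain (log-odds per SD) was 0.5 in both arms (equal), 1 in placebo and 0 in active (one arm), or 1 and −1 (opposite). Bias in the week 4 difference without the covariate, in PGIC SD units:

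| r | Equal | One arm | Opposite |
|---|---|---|---|
| 0.1 | about 0 | 0.01 to 0.02 | 0.02 to 0.04 |
| 0.3 | about 0 | 0.03 to 0.05 | 0.07 to 0.10 |
| 0.5 | about 0 | 0.06 to 0.09 | 0.11 to 0.18 |

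At the lower end of each range, half the dropouts supply a week 2 PGIC; at the upper end, none do. With baseline pain in the model, every bias was within 0.006 SD of zero.

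**The case against.** The strongest reply is that nothing is broken. Protocol and SAP agree on leaving out a baseline term, randomization makes the unadjusted contrast valid, and PGIC is one of many secondary endpoints in a Phase 2 trial with no multiplicity adjustment (SAP 4.3). A link between baseline pain and PGIC is also not assured. PGIC already rates change, and the entry rules narrow the range of baseline pain (average at least 4, no score of 10, fewer than three scores of 9), which tends to lower r. All of this stands, and it limits the point to a small improvement.

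Four stronger readings are tempting, and the documents support none of them.

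- A reader might infer that baseline pain is in every other tested efficacy model. It is stated for the primary and responder models. NePIQoL has its own baseline value, and NPSI, DSIS and the evoked-pain measures most naturally have theirs. The exploratory analyses are redacted, so no claim about them is possible.
- A reader might infer that PGIC is certainly less precise. That depends on r, which is not given and could be zero.
- A reader might infer that dropout biases the PGIC comparison. The simulation shows this only when the dependence on baseline pain differs between arms, and nothing in the documents suggests that it does. Patients lost after week 2 already contribute their week 2 score through the MMRM.
- A reader might infer that the covariate brings back patients who leave before week 2. It does not: they still supply no PGIC outcome to the model.

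What survives is that the unadjusted model has no offsetting advantage beyond about one degree of freedom, and that the substitute covariate is already derived.

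**Conclusion.** The point holds as a minor matter of efficiency and robustness. Among tested primary and secondary models with listed terms, PGIC alone has no baseline covariate, while a suitable one is on file. The planned comparison is valid.

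The variance forgone is r²: 1%, 4% and 9% at assumed r of 0.1, 0.2 and 0.3, and nothing at r = 0. The expression of this as patients per arm borrows the primary endpoint's 88 and is illustrative. Added protection against dropout matters only where the relation between dropout and baseline pain differs by arm. Under the simulated one-arm and opposite patterns at r = 0.3, the bias removed is about 0.03 to 0.10 SD; with equal dependence there is nothing to remove.

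**What to change.** In SAP 6.3.2, add the 7-day baseline NRS average defined in SAP 4.2 as a covariate in the PGIC MMRM, matching the primary model. A baseline-by-week term is optional. It would let the slope differ between weeks 2 and 4, but the primary model in SAP 6.2.2 has no such term. If the omission is deliberate, say so in SAP 6.3.2, because describing the model as similar to the primary one leaves the matter open.

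The cost is one line of SAP text and code, about one degree of freedom (one more with the interaction), and no new data. Make the change before the SAP is approved and the codes are unblinded (SAP 2.5.2), since a covariate added later could look driven by the data.

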#### 6.4. Exploratory Efficacy Analysis

## 7. SAFETY ANALYSIS

### 7.1. General

The safety population will be used for all safety analyses. Summaries will be presented by treatment group as actually received unless specified otherwise.

### 7.2. Study Drug Administration

Duration of treatment (days treated) is the number of days on treatment based on the first and last days of treatment with the study drug (last day of study drug – first day of study drug + 1). The first day of study drug and the last day of study drug will be derived from eDiary data. Total amount of study medication used at each visit (visits 4 and 5) and overall will be calculated as amount (weight in grams) of study medication dispensed minus amount of study medication returned. The expected amount of study medication usage will be calculated as (duration of treatment in days x 2 – 1) x 2 x number of dosing cards per application x 0.6 gram for visits 4 and 5; and duration of treatment in days x 2 x 2 x number of dosing cards per application x 0.6 gram for overall. Study drug compliance, derived as the percentage of total amount of study medication used divided by the expected amount of study medication usage will be descriptively summarized by treatment group for the following categories: > 120%, 100% (inclusive) - 120%, 70% (inclusive) - 100%, and < 70%. Duration of treatment (days) will also be summarized using descriptive statistics by treatment group.

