5. TREATMENT OF PATIENTS

5.1. Drugs Administered During the Study

At the baseline/randomization visit, eligible patients will be randomly assigned to 1 of 3 treatment groups (4% w/w TV-45070 ointment, 8% w/w TV-45070 ointment, or placebo ointment) as described in Section 3.4. Blinded study drug will be applied twice daily to the area of PHN pain during the treatment period from days 1 through 28, as described in Sections 3.6 and 3.11.3.

Study drug will be packaged in tubes and provided for patients to apply at home (see Section 3.6). Patients will be instructed to store the tube of ointment at ambient room temperature (15°C to 25°C) at home. Study drug exposure will be measured, and compliance to study drug administration will be monitored. Compliance will be assessed by weighing tubes at visit 3 (baseline), visit 4 (day 15 ±1, week 2), and visit 5 (day 29, week 4) or ET visit. A patient will be considered compliant during the interval between the previous 2 visits if the tube weighs between 70% and 120% of the expected weight.

Each patient will be given an eDiary and instructions on using it to record daily pain (11-point NRS), the date/time of study drug applications, and rescue medication usage. The eDiary will be used to record responses to an 11-point NRS before applying the study drug twice daily. Patients will apply the study drug in the morning after recording the morning responses to the 11-point NRS at 0700 ±2 hours, and in the evening after recording the responses to the 11-point NRS at 1900 ±2 hours.

Patients (and caregivers, as applicable) will receive instructions on how to apply the study drug. Under study site staff supervision, the area affected by PHN pain will be carefully defined by mapping the area of pain, and dosing will be prescribed to fully cover the affected area. Dosing cards and instructions will be provided on how to measure the appropriate amount of ointment for each application. A laminated instruction sheet, including pictures, will describe and illustrate how the ointment is to be spread over the entire area of PHN pain in a thin layer that fully covers the area and gently massaged into the skin.

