#### **3.4. Per Protocol Population**

The per protocol analysis set (PP) will include all patients in the FAS who 1) met all inclusion and none of the exclusion criteria, and 2) did not use > 4 days of rescue medication in baseline (days -7 to -1 prior to randomization) and last 7-day window (days 22 to 28) and did not have > 6 pills of rescue medication (1950 mg/day) for any day during that time, and 3) had at least 4 daily average NRS scores for last 7 days of treatment (days 22 to 28) and 4) had at least 70% of study medication compliance between visits 4 and 5.

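### SAP 7.2 uses the whole-treatment duration in the expected-use formula for visits 4 and 5; taken literally, a fully compliant completer scores 49% for visits 4–5 and misses the 70% per-protocol criterion

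*SAP*

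**What the plan says.** SAP 7.2 defines duration of treatment once, as "the number of days on treatment based on the first and last days of treatment with the study drug", with the formula "last day of study drug – first day of study drug + 1". The dates come from the eDiary.

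The same section then gives two expected amounts:

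- For visits 4 and 5: "The expected amount of study medication usage will be calculated as (duration of treatment in days x 2 – 1"), times 2 × cards per application × 0.6 g.
- For the whole study: "duration of treatment in days x 2 x 2 x number of dosing cards per application x 0.6 gram for overall".

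Both use the same duration term, and the SAP defines no duration for a visit interval. The amount actually used is separate for each row: "Total amount of study medication used at each visit (visits 4 and 5) and overall will be calculated" as ointment dispensed minus ointment returned. Compliance is used divided by expected, tabulated in bands with cut points at 70%, 100% and 120%.

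SAP 3.4 makes one of these figures a condition of the per-protocol set: the patient must have "had at least 70% of study medication compliance between visits 4 and 5". Protocol 5.1 has the drug "applied twice daily to the area of PHN pain during the treatment period from days 1 through 28".

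**The concern.** The numerator at each visit covers one interval of about two weeks. The denominator, on the stated definition, covers all four weeks. If a programmer inserts the one defined duration, expected use is roughly doubled at both visits and compliance is roughly halved, while the overall row stays correct.

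The visit 4–5 figure matters most because it decides entry to the per-protocol set. SAP 6.1 makes that set the supportive efficacy population. It has its own tables for the primary endpoint, evening pain, responder rate, PGIC and DSIS. The visit-level rows of the compliance table (15.3.1.2) would also be wrong.

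**Working it through.** The plan states no numerical compliance or expected amount, so there is no figure to reproduce. The check counts scheduled applications and puts them through the SAP formulas.

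**Inputs**

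- Two applications a day on days 1 to 28, so 56 in total (Protocol 5.1). Day 1 has both: the first at the site and the second that evening (Protocol 3.11.3.1).
- The morning application on the day of visit 4 is made at home before the visit (Protocol 5.1), so it belongs to the first interval and the evening one to the second.
- The last application is on the evening of day 28 (Protocol 3.11.3.1).
- Visit 4 is on day 15 ± 1 (Protocol 3.11.3.2), and study drug is collected and dispensed there.
- Assumption: 2 × cards × 0.6 g is the true amount per application, so it cancels from the ratio.

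**Applications by a completer who misses none, visit 4 on day d**

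- Up to visit 4: 2(d − 1) + 1
- Visit 4 to visit 5: 1 + 2(28 − d)

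**Literal reading.** Duration is 28 at both visits, so expected use is 28 × 2 − 1 = 55 each time.

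| Visit 4 day | Applications to visit 4 | Applications, visits 4–5 | Compliance, visits 4–5 |
|---|---|---|---|
| 14 | 27 | 29 | 29/55 = 52.7% |
| 15 | 29 | 27 | 27/55 = 49.1% |
| 16 | 31 | 25 | 25/55 = 45.5% |

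The two visit expectations sum to 55 + 55 = 110, against 28 × 2 = 56 overall.

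To reach 70% a patient would need 0.7 × 55 = 38.5 applications' worth of ointment in the second interval. That is 38.5/29 = 133%, 38.5/27 = 143% or 38.5/25 = 154% of schedule for visit 4 on day 14, 15 or 16. A completer using 120% of schedule, the top of the protocol's compliance band (Protocol 5.5), would score at most 1.2 × 29/55 = 63%.

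**Interval reading.** Replace 28 by days on drug in the interval, counting the visit 4 day in both intervals: d days, then 28 − d + 1 days.

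- Day 15: 15 × 2 − 1 = 29 and 14 × 2 − 1 = 27; compliance 29/29 and 27/27, both 100%; sum 56.
- Day 14: 27 and 29; both 100%; sum 56.
- Day 16: 31 and 25; both 100%; sum 56.

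The visit 4 day is split between the two intervals, and the subtracted 1 corrects for exactly that. With interval days, the visit formulas agree with the overall formula on every permitted visit 4 day.

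**The case against.** The strongest reply is that nobody meant the literal reading. The subtracted 1 has no purpose unless the term means interval days, and with interval days everything reconciles. The literal reading makes the sentence contradict itself, 110 applications against 56. The amount used is per visit, and the protocol repeatedly judges compliance over the interval between visits (3.6.1, 5.1, 5.5). All of this stands as evidence of intent.

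It does not make the text correct. The definition is explicit, the same words serve both formulas in one sentence, and in the overall formula they must mean the whole treatment period. The protocol's interval wording does not override this, because the SAP preface says the SAP prevails where the two differ. SAP 10, on changes to protocol analyses, does not mention compliance.

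A reader might infer that compliant completers will be removed and that the per-protocol set will select patients who over-apply. The documents do not support that as a fact: it follows only from literal programming. Such an error would also be conspicuous, with nearly every completer under 70% at both visits and about 100% overall. SAP 2.5.2 requires the analysis populations to be determined before unblinding, so there is an opportunity to catch it.

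A reader might also count the visit 4 figure (29/55 = 53% with visit 4 on day 15) against per-protocol entry. It plays no part there, since SAP 3.4 looks only at visits 4 to 5. Nor does that criterion have an upper limit; 120% comes from the protocol's compliance definition and a SAP table band.

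**Conclusion.** The point holds as a specification defect. The rule as written gives the wrong denominator for visits 4 and 5. A fully compliant completer would score 49% for visits 4–5 with visit 4 on day 15, and between 45% and 53% across the visit window, so would fail the 70% criterion. Actual loss of such patients is conditional on literal programming; interval days were very probably intended.

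The reach is limited to the supportive per-protocol set and the visit-level compliance rows. The primary analysis uses the full analysis set, which has no compliance condition (SAP 3.3), so it is unaffected on either reading.

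The percentages assume that 2 × cards × 0.6 g is what one application really uses. The documents do not give the grams per dosing card. If the true amount were half that, every percentage would halve: 24.5% literal for visits 4–5 with visit 4 on day 15, and 50% on the interval reading and overall. That is a separate question which the documents cannot settle.

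**What to change.** In SAP 7.2, for visits 4 and 5 only, replace duration of treatment by days on drug in that visit interval, and give the number of expected applications explicitly:

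- **Visit 4:** (visit 4 date − first dose date + 1) × 2 − 1.
- **Visit 5, or early termination after visit 4:** (last dose date − visit 4 date + 1) × 2 − 1.
- **Last dose before visit 4, or no visit 4:** (last dose date − first dose date + 1) × 2, without the subtracted 1.

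The third rule is needed because a patient who stops early may go straight from visit 3 to the early termination visit (Protocol 4.4), and then no day is shared between two intervals. For example, a patient whose last application is on the evening of day 10 has made 20 applications, whereas 10 × 2 − 1 gives 19.

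Multiply each by the ointment per application as now, and keep the overall formula. The cost is a wording change and a revised derivation. The dates are already collected. The change should be made before the analysis populations are determined and the codes released.
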